## **Prototype Development**

Mayo Clinic social media department will create the Facebook group page, develop the content library of moderator postings, and set up the software to capture participant use data. Existing Tips™ stories deemed culturally acceptable in the formative phase will be utilized for moderator postings. Moreover, ANTHC will develop new digital stories based on their extensive expertise. Two workshops will be held in Anchorage by two trainers with about 4-5 AN participants each, with the goal of helping individuals to generate compelling stories about their tobacco use journey. Participants will be selected from our qualitative work or by the Community Advisory Board (CAB) members and invited to participate, representing both sexes and different age groups, as well as residents of urban and rural regions. The workshops will be held over 3 days lasting about 4-8 hours each day. Each participant will sign a press release and receive a \$250 honorarium. Meals and beverages will be provided each day during the training. Instructions will be mailed to each participant prior to the workshop to bring a draft of their story of 1.5 pages or 250 words in length and photos/music they wish to incorporate. The talking circle is an integral part of story development. At the workshop, participants will first share their story in a circle to help facilitate dialogue and to obtain feedback to further develop their stories. After making revisions, each participant will privately record his or her story. Next, the trainers will edit the story with the participant to create an integrated theme consistent with the formative findings. Each story

will be 2.0-2.5 minutes as social media research indicates that the average duration a user will watch a video is 2.7 minutes.

Additional content for moderator postings will consist of images combined with text designed to provide information and stimulate participant discussion. All text will be written in the English language at a 5th grade reading level using readability analysis software. One study found that text combined with images increased Facebook engagement 84% more than text-only posts, consistent with other research. Facebook postings for optimal engagement are about 120 characters in length.

Taglines to all moderator postings will have a call to action for tobacco treatment by providing the: (1) AK state toll-free quitline number, (2) web link to regional tribal tobacco cessation programs, and (3) link to the smokefree.gov quit smoking resources website.

We will construct a content library organized similar to a treatment manual. The content library will have 30 postings to be used by the moderator once per day; and repeated for each month the group is active. In a future Stage II efficacy trial, we plan to fully automate these postings to increase intervention scalability.

The moderator will also prompt and reinforce user-generated postings and discussion (e.g., sharing of stories of tobacco use and quitting) to sustain participant engagement. Moderator guidelines for responding to participant questions and handling of inappropriate or misinformation will be included in the content library.

### **Phase 3**

#### **Beta-Testing of the Prototype**

The intervention prototype will be beta-tested with a different sample of 10 participants (eligibility criteria above). A Facebook group size of 10 was the minimum number for optimal engagement in prior work. The purpose of this phase will be to expose participants to the 30 days of moderator postings and obtain

feedback, to ensure that the system works as intended, to note any technical issues that need to be remedied, and to facilitate any refinements of the program. In the subsequent pilot trial, the Facebook group will be active for 3 months, but for this formative phase of the study, participation will be completed at the end of the 30-day beta-testing period.

An online survey will be administered at baseline to assess socio-demographics such as health literacy, age, sex, education, marital status, social media use, and tobacco use. A follow-up survey will also be administered at the end of the 30 day intervention period that includes self-reported smoking status and treatment utilization, and the Social Media Usability Measure which assesses perceived ease of use, usefulness, and satisfaction rated on a 7 point scale (1-strongly disagree, 7-strongly agree); as well as open-ended questions for feedback on modifications to the prototype. The baseline and follow-up surveys will be done online or by phone, or the survey will be mailed with a postage paid return envelope depending on participant preference. These surveys will take about 15-20 minutes each to complete. Participants will receive a \$25 gift card for completing each assessment. Refinements will be made based on user feedback.

### **Phase 4**

#### **Randomized Controlled Pilot Trial (Aim 2)**

##### **Design Overview and Considerations**

The pilot trial, a two-arm, parallel groups, randomized controlled design, will enroll 60 participants

Randomized with 1:1 allocation to the intervention or control condition. Participants will be randomized within stratified

blocks based on sex (male, female), age group (19-29, 30-49, 50+ years), and region (urban, rural); potential variables related to outcomes. Assessments will be conducted for both study groups at baseline and at 1, 3, and 6 month follow-up. The primary outcomes are feasibility indicators and the 7 day, biochemically- confirmed smoking abstinence rate at 6-month follow-up. Secondary endpoints are self-reported engagement in smoking cessation treatment and quit attempts. Table 2 compares and contrasts the two study conditions.

**Table 2: Design Elements of Study Groups**

Intervention Components	Intervention Condition Facebook Group + Quitline/Treatment Referral	Control Condition Quitline/Treatment Referral Only
Quitline/treatment referral (both groups)	Description of tobacco treatment services, phone numbers and web links sent via postal mail (printed materials) and email. Treatment options provide free, professional assistance based on U.S. clinical practice guidelines: (1) AK quitline, (2) regional tribal tobacco cessation programs, and (3) smokefree.gov resources (e.g., free texting program and smartphone application, quit guide)	
Facebook Intervention (developed in formative work)	
 
• Participants join a secret (private), culturally relevant Facebook group for 3 months, and moderated by an AN tobacco research counselor
 
• 3 months of moderator postings; plus 3-4 daily check-ins/postings to respond to participant generated content and encourage sharing of personal stories/experiences relevant to all stages of the quitting process and treatment engagement
 
	
 
• No additional intervention provided by research staff
 

[figure not shown]
**Supplemental Aim: Quantitative**

We will use the information we have learned in our previous phases to adapt existing content on COVID-19 and smoking, and conduct quantitative testing of PE among a new sample of 40 AN smokers using identical procedures and evaluation process as was done in phase 2 of the study.

*Sample.* We will enroll 40 AN smokers recruited statewide, with stratifications based on audience segment (sex, age, and location – rural or urban). Recruitment procedures and study eligibility criteria are described above. Participants meeting the eligibility criteria will be provided with details on the study and asked to provide verbal consent. Participants will receive a \$25 gift card for their time.

*FB Content.* We will use existing content (i.e., text, videos, images) on COVID-19 and smoking for adaptation from the ANTHC media department, Tips™ Campaign, and the U.S. FDA Center for Tobacco Products social media content. Informed by the cultural variance and surface/deep structure health communication frameworks, the qualitative work completed previously provided insights into cultural tailoring for new content on COVID-19 and smoking. Qualitative analyses indicated that participants preferred culturally relevant content that included images of AN people, places, and activities that told a compelling story and was emotional. Participants tended to have less interest in content that was not relatable or that included individuals who were not AN. If a story was not AN, then it needed to include AN values, such as including family/children or telling a story in a ‘real’ way, with emotion and honesty. **Figure 1** below provides an example of how we modified existing content in the parent R34 grant to be relevant to the AN culture.

**Figure 1**

We will consider additional COVID-19 relevant adaptations to existing content that may impact treatment utilization and quitting, as barriers or facilitators, including stress, anxiety, perceived risks, social isolation, and social support. The research team will select 2 videos and 4 text/image postings for adaptation and evaluation for PE. We will continue to seek technical assistance from the CDC Health Communications Branch and advice from the Community Consultation Committee in selecting new content with feedback from our moderators who are interacting with CAN Quit participants daily.

*Procedures.* Following verbal consent, we will email each eligible candidate a link to the online survey. Participants received a \$25 gift card upon survey completion. Respondents will view each of the postings then completed a 20-minute online Qualtrics (Provo, Utah, U.S.) survey assessing socio-demographic and tobacco use characteristics and an appraisal of PE of each posting using a validated measure of PE. Participants will report how much they agree with the following 6 statements for each posting: “This was worth remembering,” “This grabbed my attention,” “This was powerful,” “This was informative,” “This was meaningful,” and “This was convincing” using a 5-point scale from 1 (strongly disagree) to 5 (strongly agree). A total PE score is produced summing scores for the 6 items and dividing by the number of items in the scale (i.e., possible total score range 1=strongly disagree to 5=strongly agree); scores > 3.0 indicate greater PE. We added “This fits with my culture” to assess cultural relevance for each posting, with identical response options.

*Statistical Methods.* We will summarize sample characteristics, responses to individual items, total PE score, and the cultural relevance for each posting, with the Kruskal Wallis test to assess associations of the total PE score and cultural relevance item to sex, age group (<30, 30-49, and ≥50 years), locality (urban, rural). *P*- values ≤ 0.05 will be considered statistically significant. Postings with PE > 3.0, no substantive differences across demographic groups, and with elements considered salient to AN people who smoke, will be added to the FB intervention content library.

Interventions

All participants will receive evidence-based tobacco treatment referral information by postal mail (printed materials) and email, including information on their regional tribal tobacco treatment program, state quitline, and smokefree.gov quit smoking resources (see Table 2).

Control condition will receive no additional intervention provided by research staff.

Intervention condition will additionally receive the Facebook intervention developed in Aim 1. With the enrollment letter, participants will receive instructions for joining the Facebook group. The Facebook group will be moderated on a daily basis by an AN tobacco research counselor who will be trained onsite in Anchorage by Drs. [name] and [name] using didactics and mock Facebook postings; a “refresher” training will occur 6 months after the initial training. The research team will develop a written guide for how often the moderator

should log in with expectations for his/her engagement. Moderators will also enhance engagement through prompting discussion of cultural identity and how that relates to smoking through various Facebook methods

Table 3: Pilot Trial Measures	Baseline	1, 3, & 6 Months
Socio-demographics and tobacco use	X	
Feasibility measures (e.g., retention, Facebook use and engagement)		X
Self-reported smoking abstinence		X
Self-reported tobacco/nicotine product use	X	X
Saliva cotinine: to verify smoking abstinence		X
Self-reported smoking treatment utilization		X
Communal Orientation Scale (mediator)	X	X

(e.g. Facebook poll, comments). A potential concern about using social media for health interventions is that user postings may be of poor quality, for example, inconsistent with clinical practice guidelines or involve inappropriate or illegal activities. When participants enter the study they will be informed about the policies for posting content and that any inappropriate postings will be removed. In [name] trial, less than 1% of postings were inappropriate. The moderator will be trained to handle inappropriate or misinformation and to direct information content toward evidence-based information exchange and social support. A random

sample of 20% of moderator postings and responses to participant inquiries and discussions will be selected every week for the first four weeks and monthly thereafter. These transcripts will be coded by [name] to assess moderator adherence to the proscribed intervention. Feedback will be provided to the moderator during weekly research team teleconferences.

### Measures

Assessments (see Table 3) will be completed at baseline and 1, 3, and 6 months follow-up. Missing data will be minimized through online assessments. With the exception of obtaining a saliva specimen for cotinine analysis, all measures will be administered online using Qualtrics. An email link will be sent automatically by the Mayo Clinic Survey Research Center to complete the assessment. If a participant does not complete online assessments, he/she will be contacted through email or by phone by the project coordinator and prompted to complete the assessment. The baseline and follow-up surveys will be done online, by phone, in person, or the survey will be mailed with a postage paid return envelope depending on participant preference. These surveys will take about 15-30 minutes each to complete. Participants will be mailed a \$25 Visa gift card as remuneration for completing each assessment, the intervention group will receive their initial \$25 Visa gift card after they complete the baseline assessment and join the Facebook group.

Socio-demographic and tobacco use characteristics. At baseline, we will assess participants' health literacy, sex, age, tribal group, cultural identity (language, traditionalism), region of residence, marital status, education, employment, and current frequency of use of Facebook and other social media platforms. Tobacco use measures will include cigarettes per day, years of smoking, readiness to quit (Contemplation Ladder), use of other tobacco and nicotine products, and the time to first cigarette after waking <30 minutes vs. ≥30 minutes, which is primarily consistent with the 6-item Fagerström Test for Cigarette Dependence.

Feasibility measures. To assess feasibility and reach, we will collect data on: # screened, # eligible based on the inclusion/exclusion criteria, # of eligible participants enrolled, and reasons for exclusion or non-

participation.

The proportion of 60 participants completing the 6 month follow-up assessment (i.e., retention) and the proportion providing a saliva cotinine specimen at each assessment will also be summarized. Treatment acceptability will be assessed with brief intervention satisfaction rating scales.

Data from the Facebook application programming interface will be extracted using Sprinklr software. For each week of the study, we will extract for each intervention participant the following engagement metrics: # of logins; # digital story downloads; # user-generated posts, comments, questions and responses to the moderator or other users; # likes, shares and reactions; and time and date of each. In addition, a transcript of all participant postings will be generated for content analysis.

Smoking abstinence. At each follow-up, we will obtain the participant's self-reported cigarette use in the past 7 and 30 days, number of cigarettes smoked per day, and quit attempts. We will also assess current use of ST/*iqmik*, e-cigarettes, and other tobacco/nicotine products. All participants will be mailed a saliva kit with a collection tube and postage paid return envelope. Participants returning a saliva specimen will receive an additional \$25 Visa gift card. The specimen will be shipped to and assayed by Mayo Clinic laboratories. This approach has been feasible in several NIH-funded clinical trials conducted in AK (DA 025156; CA164533; CA153605) and in other studies; and biochemical verification is recommended in randomized trials with sample sizes under 500. Point prevalence smoking abstinence will be defined as no smoking (not even a puff) for the last 7 days verified with salivary cotinine level <15 ng/ml. Use of nicotine replacement therapy and ST/*iqmik* use will be assessed at follow-up because its use would elevate cotinine concentrations. If participants indicate use of e-cigarettes, saliva cotinine and reported e-cigarette use will be recorded and analyzed separately from biochemically verified cigarette smoking abstinence.

Smoking Treatment Utilization. As a secondary aim, we will document self-reported use of any evidence-based cessation aid during the 6 month study period. For this pilot study, it is not practical to objectively verify self-reported treatment use given heterogeneity of potential services/medications used.

Communal Orientation Scale (COS). The 14-item validated COS will be administered at baseline and follow-up to examine interdependence as a culturally relevant mediator of intervention efficacy. In the intervention condition, we will also explore association of COS baseline scores with Facebook engagement. This measure assesses the extent to which individuals are relationship-versus self-oriented.

Coronavirus (COVID-19). At the 6 month follow-up assessment we will obtain information on the impacts of COVID-19 on smoking treatment and cessation. For those receiving the Facebook intervention we will also obtain satisfaction with the COVID-19 content and conversation.

### Sample Size Calculation

The goal of the pilot trial is to obtain effect size estimates to adequately power a larger scale, Stage II efficacy trial. A sample size of 60 enrolled will be sufficient to determine the intervention's feasibility. Although not able to detect statistically significant study group differences on smoking abstinence, the study can obtain estimates of the intervention effect towards planning a definitive Stage II efficacy trial. For the dichotomous variable of point prevalence abstinence, 30 subjects per condition should provide relatively stable group proportions for effect size estimates. Effect size estimates will include odds ratios for smoking abstinence. In addition to demonstrating feasibility, a doubling of the abstinence rate for the intervention vs. control condition at 6 months will be considered to be of clinical significance and

warrant proceeding to an efficacy trial. This approach is consistent with recommendations for Stage I work in behavioral addictions treatment development and for conducting small-scale trials to advance e-health interventions. Given the small sample size, proposed mediational analyses are exploratory.

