### Data Analysis Plan

Recruitment data will be summarized, including the number of potential participants screened, number excluded for each inclusion/exclusion criteria, and number of eligible individuals agreeing to participate. To assess program reach, we will calculate proportion of subjects enrolled to total eligible subjects and compare enrollment rates by region (rural or urban) using the chi-square test. Baseline demographics will be summarized and compared between study groups using the chi-square test for categorical variables and the two-sample t-test/rank sum test for continuous variables. Percentage of enrolled participants completing each follow-up assessment (i.e., study retention) and ratings of treatment acceptability will be compared between study groups using the chi-square test (Fisher's exact test). Facebook use and engagement will be summarized using descriptive statistics and time effects over the 3 month treatment period will be assessed via mixed effects models as appropriate to explore sex, age group, and region effects respectively. The association of COS baseline scores and Facebook engagement will be evaluated using linear regression. Qualitative (content) analysis will be utilized to generate themes in Facebook postings and comments.

Biochemically-confirmed 7-day point prevalence tobacco use rate at 1, 3, and 6 months follow-up will be compared between conditions using logistic regression (with odds ratio and 95% confidence interval estimates). Using an intent-to-treat approach, we will classify as smoking participants eligible but lost to follow-up or not providing biochemical verification of smoking abstinence. We will also explore multiple imputation methods to classify lost to follow-up as cigarette smokers or non-smokers and conduct sensitivity analyses as appropriate. For these analyses, we will adjust for stratification factors (sex, age group, urban/rural region) and any baseline differences observed between treatment conditions if data allow (i.e., adequate numbers of subjects verified as abstinent). Secondary analyses using logistic regression will explore intervention effects on self-reported abstinence from all tobacco/nicotine products, quit attempts, and self-reported tobacco treatment utilization. We will follow procedures suggested by MacKinnon to assess mediation, fitting logistic/linear regression models to the data.

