## Data Analysis

**Power Statement:** For the pilot RCT, the goal is to obtain effect size estimates to adequately power a larger scale, Stage II efficacy trial. Our recommended sample size, 60 enrolled AN people who smoke, will be sufficient to determine the intervention's feasibility. We recognize that the study is not adequately powered to detect statistically significant group differences on smoking abstinence, but we seek to obtain estimates of the intervention effect towards planning a definitive Stage II efficacy trial.

**Data Analysis Plan:** Recruitment data will be summarized, including the number of potential participants screened, number excluded for each inclusion/exclusion criteria, and number of eligible individuals agreeing to participate. To assess program reach, we will calculate proportion of subjects enrolled to total eligible subjects and compare enrollment rates by region (rural or urban) using the chi-square test. Baseline demographics will be summarized and compared between study groups using the chi-square test for categorical variables and the two-sample t-test/rank sum test for continuous variables. Percentage of enrolled participants completing each follow-up assessment (i.e., study retention) and ratings of treatment acceptability will be compared between study groups using the chi-square test (Fisher's exact test). Facebook use and engagement will be summarized using descriptive statistics and time effects over the 3 month treatment period will be assessed via mixed effects models as appropriate to explore sex, age group, and region effects respectively. The association of COS baseline scores and Facebook engagement will be evaluated using linear regression. Qualitative (content) analysis will be utilized to generate themes in Facebook postings and comments.

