Biochemically- confirmed 7-day point prevalence tobacco use rate at 1-, 3-, and 6-months follow-up will be compared between conditions using logistic regression (with odds ratio and 95% confidence interval estimates). Using an intent-to-treat approach, we will classify as smoking participants eligible but lost to follow-up or not providing biochemical verification of smoking abstinence. We will also explore multiple imputation methods to classify lost to follow-up as cigarette smokers or non-smokers and conduct sensitivity analyses as appropriate. For these analyses, we will adjust for stratification factors (sex, age group, urban/rural region) and any baseline differences observed between treatment conditions if data allow (i.e., adequate numbers of subjects verified as abstinent). Secondary analyses using logistic regression will explore intervention effects on self-reported abstinence from all tobacco/nicotine products, quit attempts, and self-reported tobacco treatment utilization. We will follow procedures suggested by MacKinnon to assess mediation, fitting logistic/linear regression models to the data.

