## **Data Safety Monitoring Plan (DSMP)**

### **Power Calculation and Sample Size**

Sample size for each stage of this research was guided by guidelines for behavioral treatment development research. For the formative work we calculated the number of interviews necessary to cover the major subsets of interest based on audience segment (gender, age, region) and to achieve data saturation, whereby no new information is being gained by adding participants.

For the pilot RCT, the goal is to obtain effect size estimates to adequately power a larger scale, Stage II efficacy trial. Our recommended sample size, 60 enrolled AN people who smoke, will be sufficient to determine the intervention's feasibility. We recognize that the study is not adequately powered to detect statistically significant group differences on smoking abstinence, but we seek to obtain estimates of the intervention effect towards planning a definitive Stage II efficacy trial. For the dichotomous variable of point prevalence abstinence, 30 subjects per condition should provide relatively stable group proportions for effect size estimates. Effect size estimates will include odds ratios for smoking abstinence. In addition to demonstrating feasibility, a doubling of the abstinence rate for the intervention vs. control condition at 6 months will be considered to be of clinical significance and warrant proceeding to an efficacy trial. This approach is consistent with recommendations for Stage I work in behavioral addictions treatment development and for conducting small-scale trials to advance e-health interventions. Given the small sample size, proposed mediational analyses are exploratory.

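### Thirty per condition does not give stable abstinence proportions or effect sizes, and the 6-month doubling criterion is read on a point estimate alone

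*Combined protocol and SAP*

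**What the plan says.** The Phase 4 Sample Size Calculation sets the purpose: "The goal of the pilot trial is to obtain effect size estimates to adequately power a larger scale, Stage II efficacy trial". It concedes the limit on testing: "Although not able to detect statistically significant study group differences on smoking abstinence, the study can obtain estimates of the intervention effect". It then justifies the arm size by saying that "30 subjects per condition should provide relatively stable group proportions for effect size estimates", with no assumed rate, interval width or precision target. The progression criterion follows: "In addition to demonstrating feasibility, a doubling of the abstinence rate for the intervention vs. control condition at 6 months" is treated as clinically significant and as grounds for an efficacy trial.

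The DSMP section Power Calculation and Sample Size repeats both the stability sentence and the criterion, which "will be considered to be of clinical significance and warrant proceeding to an efficacy trial". The Power Statement under Data Analysis has the same goal, saying "we seek to obtain estimates of the intervention effect towards planning a definitive Stage II efficacy trial", but makes no stability claim.

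The Data Analysis Plan, which appears twice, compares abstinence by logistic regression "with odds ratio and 95% confidence interval estimates". It counts participants who are lost or unverified as smoking, and adjusts for covariates only "if data allow (i.e., adequate numbers of subjects verified as abstinent"). Neither version says how the interval bears on the doubling.

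**The concern.** Conceding that a study cannot detect a difference is not the same as conceding that its estimates are imprecise. The plan does the first and then asserts roughly the opposite of the second. The stability sentence is the only statistical reason given for 30 per arm on abstinence, which is a primary outcome, and the doubling is the only numeric progression criterion.

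Two uses depend on these proportions: the decision to proceed, and the stated goal of supplying effect sizes to power Stage II. If the observed rates can be several-fold off, an observed doubling says little about whether the true rate doubled, and the pilot odds ratio is a poor basis for sizing the next trial.

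**Working it through.** There is no sample size formula in the plan to reproduce; 30 per arm is asserted. The check is of the precision it gives.

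**Inputs.** n = 30 per arm (60 enrolled, 1:1). Missing counts as smoking, so the denominator stays at 30. The criterion is a ratio of 6-month rates of at least 2. No control rate is stated. I assume 4-20%, from two imperfect proxies in the Literature Review: 4% is the figure for successful quitting among Alaska Native adults, and 20% is the 2-month self-reported control rate in the Twitter trial, whose controls received nicotine patches. Participants are treated as independent; clustering within the Facebook group would usually widen the intervals.

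**1. Precision of one proportion (no assumed rate needed).** Exact Clopper-Pearson limits for x/30 are the 2.5% point of Beta(x, 31-x) and the 97.5% point of Beta(x+1, 30-x).
- 3/30 (10%): 2.1% to 26.5%
- 6/30 (20%): 7.7% to 38.6%

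**2. Precision of the odds ratio at an exact doubling.** ln OR ± 1.96 × SE, with SE = √(1/a + 1/b + 1/c + 1/d). This is the Wald interval of the unadjusted logistic regression.
- 6 vs 3: OR = (6×27)/(3×24) = 2.25; SE = √(1/6 + 1/24 + 1/3 + 1/27) = 0.761; 95% CI 0.51 to 9.99
- 12 vs 6: OR = (12×24)/(6×18) = 2.67; SE = √(1/12 + 1/18 + 1/6 + 1/24) = 0.589; 95% CI 0.84 to 8.46

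**3. How often a doubling is observed.** Sum the joint probability of two independent binomials, X_C ~ Bin(30, p) and X_I ~ Bin(30, p) or Bin(30, 2p), over outcomes with X_I ≥ 2·X_C and X_I > 0. An outcome with no control quitter and any intervention quitter therefore counts. The last column is (1-p)^30.

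| Control rate (assumed) | No effect | True doubling | No control quitters |
|---|---|---|---|
| 4% | 34% | 58% | 29% |
| 7% | 31% | 58% | 11% |
| 10% | 25% | 57% | 4% |
| 20% | 13% | 55% | 0.1% |

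These concern the doubling alone. Feasibility is also required, so they are upper bounds on the chance of proceeding.

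**4. Stage II size on the pre-specified doubling.** Pooled two-proportion formula; two-sided 5% and 80% power are assumed, since the plan gives neither for Stage II. At 10% vs 20%, with mean rate 0.15: n = [1.96·√(2×0.15×0.85) + 0.842·√(0.09+0.16)]² / 0.10² = (0.990 + 0.421)²/0.01 ≈ 199 per arm. The same formula gives 553 at 4% control, 300 at 7% and 82 at 20%. The control rate alone moves the answer nearly sevenfold (553/82 = 6.7).

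**The case against.** The best defence is that the plan is candid. It says three times that the pilot cannot detect group differences, calls the mediation work exploratory because of the small sample, and already plans a 95% CI that will display the imprecision. On that view all that remains is one hedged phrase, and relative stability has no numeric threshold to fail. This stands in part: no stated number is wrong, and the power concession is correct. It does not rescue the sentence, because low power for a test and stability of an estimate are separate properties, and the second is the one asserted as the basis for n.

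Some stronger readings are tempting but not supported:
- A reader might infer that the criterion fails because the interval at a doubling includes 1. That returns to significance, which the plan concedes; requiring exclusion of 1 would be out of reach for most doublings at this size.
- A reader might infer that a doubling alone triggers progression. The text requires feasibility as well.
- A reader might infer that Stage II will be sized on the observed pilot odds ratio. The goal statement leaves that open; no section says so.
- A reader might take the condition on covariate adjustment as an admission that few abstainers are expected. It is a contingency for model fitting and no more.

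**Conclusion.** The point holds as a matter of stated precision and of how one criterion is worded. It does not show that the trial is too small for a pilot. At 30 per arm, plausible abstinence counts leave each proportion uncertain by a factor of about 5 (38.6/7.7 at 6/30) to about 12 (26.5/2.1 at 3/30), and an observed doubling is compatible with anything from a reduced odds of quitting to an eight- to tenfold increase. Those figures need no assumed rate.

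The operating characteristics do depend on the assumed 4-20% control range and on counting zero-control outcomes. Under those assumptions the doubling is met in about 13-34% of trials with no effect and 55-58% with a true doubling, so on its own it discriminates weakly. The importance is minor to moderate: the trial can run as designed, but the stated basis for n and the progression criterion could mislead those planning Stage II.

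**What to change.** 1. In the Sample Size Calculation and the DSMP's Power Calculation and Sample Size section, replace the stability sentence with the actual precision. For example: with 30 per condition, 3/30 has a 95% CI of 2-27% and 6/30 of 8-39%; observed doublings of 6 vs 3 and 12 vs 6 give odds ratios of 2.25 (0.51-9.99) and 2.67 (0.84-8.46).
2. In the same two sections, state that the observed doubling will be reported with the 95% CI already planned in the Data Analysis Plan, and that a point-estimate doubling together with feasibility is supportive but does not by itself warrant proceeding. Do not require the interval to exclude 1.
3. In those two sections and in the Power Statement under Data Analysis alike, state that the pilot informs the control rate, retention and feasibility, and that Stage II will be sized on the pre-specified doubling over a range of control rates, not on the observed pilot odds ratio. All three goal statements must change together or they will disagree.

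A convention for zero control quitters may be written down, but it is secondary. Avoid a rule that treats every such outcome as not meeting the doubling: it would fail 6 vs 0 while passing 2 vs 1.

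The cost is wording only, with no extra participants, visits or data. The downside is real: the stated precision looks less favourable, and the pilot no longer claims to supply the Stage II effect size, which changes a stated objective.
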